Rationale	
Noncytotoxic dosing of decitabine given weekly at a dose of 0.2 mg/kg induces depletion of DNA methyltransferase 1 (DNMT1) while minimizing the toxicity and myelosuppression seen with standard HMA dosing regimens. This approach has been shown to be effective in a wide spectrum of patients with myeloid malignancies, including patients with resistant disease such as P53 mutations.
 
Preclinical studies have demonstrated that adding a dose of venetoclax prior to administering decitabine enhances the anti-leukemic activity of HMAs by inhibiting de novo pyrimidine synthesis, which is a major mechanism of resistance to HMA in MDS/AML. Decreasing the dose of venetoclax to a weekly schedule also spares normal myelopoiesis. Therefore, a weekly dosing of decitabine/venetoclax is a very attractive option for a patient population who cannot tolerate or are not known to benefit standard Aza/ven.

Primary Objective	
Primary Endpoint
 
Percentage of participants who are able to continue on treatment without dose interruptions or delays. Defined as delaying or interrupting treatment due to toxicity or intolerance during the induction phase (weeks 1-12)

Secondary Objective(s)	
Secondary Endpoints: (1) Cumulative incidence of response for both CR, CRI and overall response; (2) Event free survival

	
(EFS); (3) Complete remission or complete remission with partial hematologic recovery rate (CR+CRh); (4) Post baseline transfusion dependence rate; (5) Fatigue/quality of life (QoL); (6) Rate of hospitalization; (7) Infection rate
 
Scientific Correlates:
 
Correlation of DNMT1 depletion with clinical response criteria

Sample Size	85 patients
Disease sites/Conditions	Myeloid malignancies: ≥MDS, AML, MDS/MPN overlap syndrome
• Interventions	
 • Venetoclax 400 mg po on days 1, 8, 15 and 28 of each cycle (28day cycle) (+/- 1 day allowed). • Decitabine 0.2 mg/kg SQ on days 1, 8, 15, 22 (for aggressive disease will add decitabine on days 2, 9, 16, 23)

TABLE OF CONTENTS

SUMMARY OF CHANGES	3
ABBREVIATIONS.....	5
STUDY SCHEMA	6
PROTOCOL SUMMARY	7
TABLE OF CONTENTS	9
1.0 INTRODUCTION	12
1.1 BACKGROUND.....	12
1.1.1 Diseases- Myeloid malignancies: Acute Myelogenous Leukemia (AML) and Myelodysplastic Syndromes (MDS) and Myeloproliferative neoplasms (MPN).....	12
1.1.2 Treatment of myeloid malignancies	12
1.2 STUDY RATIONALE.....	14

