2.2 Secondary Objective(s)

1. Percentage of MDS participants with complete remission (CR) and complete remission with incomplete marrow recovery (CRi)
2. Percentage of AML participants with complete remission (CR) and complete remission with incomplete marrow recovery (CRi)
- 3.

This will be calculated based on current International Working Group (IWG) criteria. CR is defined as absolute neutrophil count $> 1000/\text{microliter (mCL)}$, platelets $> 100k/\text{mCL}$, red cell transfusion independence, and bone marrow with $< 5\%$ blasts. CRi is defined as bone marrow with less than 5% blasts, and absolute neutrophils of $\leq 10000/\text{mCL}$ or platelets $\leq 100k/\text{mCL}$

4. Event-free survival (EFS)

EFS will be defined as the number of days from randomization to the date of progressive disease, relapse from CR or CRi, treatment failure or death from any cause.

5. Complete remission or complete remission with partial hematologic recovery rate (CR+CRh)

A response of CRh is defined as Bone marrow with $< 5\%$ blasts, peripheral blood neutrophil count $> 0.5 * 10^3/\text{mCL}$ and peripheral blood platelet count $> 0.5 * 10^5/\text{mCL}$.

6. Post baseline transfusion independence rate

Transfusion Independence is defined as a period of 56 days with no transfusion between first dose of study drug and the last dose of study drug + 30 days. The rate of conversion for red blood cells (RBC) and platelets is defined as percentage of participants being post-baseline transfusion independent from baseline transfusion dependence.

7. Rate of Hospitalization

Defined as hospitalization for complication related to myeloid malignancy or treatment. Initial admission for diagnosis or initiation of therapy will not be considered an event.

8. Infection rate requiring hospitalization

Defined as being hospitalized due to an infection or sepsis.

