6.4 Duration of Follow Up

The evaluation of the primary and secondary endpoints of ORR, CIR, and DOR are continuous. If in the judgement of patients and the treating clinical team, patients are benefiting from this therapy, the therapy will be continued even after measurement of the primary end-point at week 12 but monitoring will continue every 4 weeks or more often if clinically indicated. Patients will be considered off-protocol monitoring if they develop relapsed or progressive disease.

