endpoints of efficacy in MDS and AML. This additional data may help in the design subsequent studies which will require adding an additional agent to this regimen as a backbone as it's becoming increasingly clear the HMA/VEN does not have a cure rate²⁵ and the way forward will require a third effective agent with multiple trials now evaluating triplets and using HMA/VEN as a backbone. The comparator arm for HMA/VEN in all trials is the current standard of single agent HMA (Azacitidine or Decitabine).

The expansion phase will be stratified by disease type, i.e., MDS and AML.

Single agent HMA has a 16% CR rate in MDS.²⁶ The CR rate with HAM/VEN is expected to be at least 36%. The target sample size for the MDS group will be a total of 32 patients (from both initial and expansion phases). With this sample size, we can estimate the CR rate with standard error no greater than 9%.

In AML, single agent HMA has a CR rate of 17.9%.¹ The CR rate with HAM/VEN is expected to be at least 38%. With a total of 38 AML patients from both phases, we can estimate the CR rate with standard error no greater than 8%.

In summary, an amendment will be added for additional 42 patients (above the originally planned 33 patients) with either MDS or AML after accounting for drop-outs. For example, if we assume among the first stage of 33 patients, we have 16 MDS, 17 AML, then the study needs enroll additional 16 MDS and 21 AML, a total of 37 patients. Allowing up to 5 patients to drop out from the study and the study may also enroll approximately 10 patients with other rare myeloid malignancies such as CMML and MDS/MPN. We therefore expect the total number of patients needed to be enrolled in the study to be not more than 85 (33+37+5+10) patients.

Safety: Incidence of treatment-emergent adverse events will be tabulated severity/grade, and whether the AE resulted in death or discontinuation of treatment.

Early Stopping Rule for Excessive Toxicity in Expansion Phase: We will continue using Bayesian toxicity monitoring in the expansion phase, similar to what was described in the initial stage of the study (Sec 6.6), to allow for early stopping due to excessive toxicity.

Laboratory data will be summarized in tables that show changes from pre-treatment values and frequencies of abnormal values. Descriptive statistics will also be provided.

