Efficacy: The primary end-point of a decrease in dose interruptions will be described as proportion of patients point-estimates, together with the corresponding 95% confidence interval. Kaplan-Meier method will be used to summarize time to event variables.

Secondary end-points and scientific correlative studies: For the secondary end-points and scientific correlates (secondary objectives), either logistic regression or correlation analysis will be utilized to examine and assess the relationships and predictive nature of these biological parameters on hematologic improvement and ability of decitabine/ven to deplete DNMT1 in malignant cells, and the alteration of pyrimidine metabolism. Descriptive summaries of the data will be provided.

Accrual rate: Estimated accrual rate of 1-3 patients per month with approximately 18-24 months to meet total accrual goals, and additional 3 months to observe primary outcome measures. DOR of response will be followed for up to two years, thus a total of three to four years is anticipated to meet all study endpoints.

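### Cumulative incidence of response is a listed endpoint, but Section 13 names only Kaplan-Meier and gives no handling of death or progression before response

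*Combined protocol and SAP*

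**What the plan says.** The documents describe the response endpoint in more than one way.

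- The Protocol Summary, under secondary endpoints, lists first "Cumulative incidence of response for both CR, CRI and overall response".
- Section 2.2 gives CR and CRi as a percentage of MDS participants and, separately, of AML participants. No time axis is mentioned.
- Section 6.4 states "The evaluation of the primary and secondary endpoints of ORR, CIR, and DOR are continuous". CIR is not expanded there or in the abbreviation list, so it could mean incidence of response or of relapse.
- Section 13, under Efficacy, states "Kaplan-Meier method will be used to summarize time to event variables". It does not list which endpoints those are.
- Section 13 sizes the expansion on the precision of a CR rate: standard error at most 9% with 32 MDS patients and an expected rate of 36%, and at most 8% with 38 AML patients and an expected rate of 38%.

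On what happens to patients who fail before responding, Section 6.4 says "Patients will be considered off-protocol monitoring if they develop relapsed or progressive disease". Section 2.2 defines EFS as running to the "date of progressive disease, relapse from CR or CRi, treatment failure or death from any cause". No section names a competing-risks estimator or gives a censoring rule for time to response.

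**The concern.** A patient who dies without responding can no longer respond. A patient who progresses leaves protocol monitoring under Section 6.4, so a later response would not be seen. A routine Kaplan-Meier analysis of time to response would censor both at their last assessment, which treats them as still able to respond at the same rate as those who remain under observation. One minus that curve is never below the cumulative incidence, so any error favours the regimen.

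The situation is a plausible one here. Section 6.1 notes that maximal response to HMAs can take six months or longer, and Section 4.1 admits patients with ECOG status up to 3, so some failures before response are to be expected. Section 1.4 (rationale for cohort expansion) says the efficacy data are meant to guide sample sizes for later studies, so an inflated response curve could be carried forward.

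**Working it through.** **Step 1: the plan's own precision figures.** Inputs are from Section 13. The binomial standard error is sqrt(p(1−p)/n).

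- MDS: sqrt(0.36 × 0.64 / 32) = 8.49%, against a stated bound of 9%.
- AML: sqrt(0.38 × 0.62 / 38) = 7.87%, against a stated bound of 8%.

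Both reproduce as simple proportions. The quantity that sizes the expansion is therefore not a Kaplan-Meier estimate.

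**Step 2: direction of the bias.** Let H1(t) and H2(t) be the cumulative cause-specific hazards of response and of death or progression before response. The cumulative incidence adds up exp(−H1−H2) dH1. One minus Kaplan-Meier, with the second type of event censored, adds up exp(−H1) dH1. The second integrand is never smaller, so the direction holds for any rates.

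**Step 3: size.** Let F1 be the true incidence of response and F2 the incidence of death or progression first, both by the same time. With constant hazards,

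- H1 = −ln(1 − F1 − F2) × F1 / (F1 + F2)
- 1 − KM = 1 − exp(−H1)

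F1 is taken as the expected CR rates in Section 13, which carry no time horizon. F2 is assumed to lie between 5% and 30%, because the documents give no figure.

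Worked example, AML with F2 = 10%: H1 = −ln(0.52) × 0.38/0.48 = 0.6539 × 0.7917 = 0.5177, and 1 − exp(−0.5177) = 40.4%.

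| Assumed F2 | MDS, true 36% | Excess (points) | AML, true 38% | Excess (points) |
|---|---|---|---|---|
| 5% | 37.1% | 1.1 | 39.1% | 1.1 |
| 10% | 38.3% | 2.3 | 40.4% | 2.4 |
| 20% | 41.0% | 5.0 | 43.4% | 5.4 |
| 30% | 44.5% | 8.5 | 47.1% | 9.1 |

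With F2 = 0 the excess is zero.

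**Step 4: dependence on timing and handling.** Take 38 AML patients with 14 responders, a proportion of 14/38 = 36.8%, and otherwise complete follow-up. If four patients fail before any response occurs and are censored then, one minus Kaplan-Meier is 14/34 = 41.2%. If the same four are kept in the risk set to the end of follow-up, it is 14/38 = 36.8%. The bias comes from the censoring, and it is larger when failures come early.

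**The case against.** The strongest reply is that response is not planned as a time-to-event variable at all. Section 2.2 defines CR/CRi as percentages, Section 13 plans precision for a proportion, and Section 1.4 reports interim AML response as 7/11, or 64%. The Kaplan-Meier sentence is satisfied by EFS and duration of response. A separate paragraph of Section 13 covers secondary endpoints by logistic regression or correlation, with descriptive summaries. No section announces a response curve.

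Much of this stands, and it rules out three stronger readings that a reader might infer:

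- That response will be overstated. The documents neither assign Kaplan-Meier to response nor say that failures are censored, so the text supports only that it can be.
- That the efficacy result for which the expansion was sized is biased. That result is a binomial CR rate, which this problem does not touch. For the same reason the 8% and 9% standard errors are not a proper yardstick for the excess in the table; they belong to a different estimator.
- That Kaplan-Meier is prescribed for every time-based endpoint. The sentence is general and lists none.

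It can also be argued that progression need not be a competing event, since the removal criteria in Section 6.3 suggest that some patients may continue after progression, whereas Section 6.4 ends monitoring at that point. Those two sections must be reconciled, and the handling of progression in the analysis should then be stated.

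The reply does not remove the Protocol Summary line. A cumulative incidence of response is a named endpoint, and the only time-to-event method on offer does not suit it.

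**Conclusion.** The point holds as a conflict between definitions together with a missing estimator. The Protocol Summary calls for a cumulative incidence, Section 2.2 for a percentage, and Section 13 supplies no method fit for the former. If it were estimated as one minus Kaplan-Meier with death and progression censored, the overstatement would be about 1 to 9 points at response levels of 36% to 38%. That size rests on constant hazards and on an assumed 5% to 30% of patients failing before response; it is only 1 to 2 points at the lower end of that range. The direction does not depend on these assumptions.

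The endpoint is secondary and no test is attached to it. The primary test, the sample size and the binomial CR rates are unaffected. Kaplan-Meier is suitable for EFS, because its definition already counts progression and death as events.

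**What to change.** In Section 13, state the following:

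- CR and CRi rates are reported as binomial proportions with all treated patients in the denominator. The denominator needs stating because Section 3.2 allows some patients to be replaced.
- Cumulative incidence of CR, CRi and overall response is estimated by the Aalen-Johansen method, with death and progression without response as competing events.
- Kaplan-Meier is used for EFS.

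Align the Protocol Summary and Section 2.2 so that each names both summaries, or whichever one is kept. Spell out CIR in Section 6.4; if it means relapse, treat death in remission as a competing event.

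The cost is a few sentences. No additional patients or assessments are needed. The response curve may look slightly less favourable than a Kaplan-Meier version would.
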